7.2 Blinding mechanism

Blinding will be performed by personnel assigned by the Clinical Operations Management of Laboratorios Sophia SA de CV. This will consist of identical labeling for both interventions. This will prevent the PI, the study subject, and all unauthorized individuals from identifying which intervention each container belongs to.

7.3 Implementation

The sequence will be generated using an electronic randomization system. This system will be contracted by Laboratorios Sophia , SA de CV to a third party. Information about this third party will be found in the study's master folder.

7.4 Blinding (Masking)

Blinding will be performed on the subject and principal investigator. Furthermore, the statistical analysis will be performed blindly for the partial and final analyses.

Blinding will be carried out using identical labels. These, in compliance with current and applicable regulations, must contain at least:

- Name, address and telephone number of the sponsor
- Pharmaceutical form and route of administration
- Batch number
- Legend "Exclusively for clinical studies"
- Expiration date

7.4.1 Opening the blind

Blinding may be opened in the following cases:

1. Presence of a serious adverse event.
2. Safety alert for the use of the drugs under study.

3. In the event that the sponsor determines it for any security reason or other reason that it deems appropriate.

8. Methods. Data collection, management, and analysis

8.1 Data collection methods

The sponsor will assign a clinical monitor to the research site, who will be authorized to monitor, review, procure, and ensure that the quality of the information obtained from participants is reliable and trustworthy. The monitor will schedule periodic visits to the research sites to review source documents and corroborate the information captured in the case report form (CRF). The monitor will be trained in the study protocol information (objective, visits, procedures, accepted range of values, etc.). If the data are not identical between the two records, the clinical monitor will generate a discrepancy, which must be resolved by the research site within the timeframe the sponsor deems reasonable to meet the objectives of the clinical study. Discrepancies will be corrected in accordance with Good Documentation Practices.

The data recorded in the CRF will be reviewed by Laboratorios Sophia , SA de CV personnel trained in ophthalmology, clinical, and pharmacology, who will have the authority to generate discrepancies in the event that the data do not adhere to the provisions of the research protocol or put participants at risk.

Once all discrepancies generated by the clinical monitoring team and clinical staff have been resolved , the data will be downloaded into an electronic database (Excel spreadsheet) by personnel designated by the sponsor. A new review of the data will be conducted to verify its accuracy, and new discrepancies may be generated if deemed necessary.

The generated database will be safeguarded by the sponsor and will only be accessible to designated personnel.

8.1.1 Strategies for completing the follow-up

- You will be clearly informed of the importance of the study and the benefits the population will gain from its results.
- Transportation assistance will be provided to enable participants to attend their visits.
- A printed calendar will be provided to remind participants of their appointments and upcoming activities, as well as their estimated duration.
- If the participating subject does not attend their appointment, the research site will call to determine the reason and will attempt to schedule a new appointment within the established window or an unscheduled appointment. (If an appointment cannot be scheduled, the presence of adverse events and the reason for discontinuing the study will be asked as minimum information.)

8.2 Data Management

The subject's medical record (including clinical notes, examination results, etc.), as well as the subject's diary, and the ICO questionnaire are considered source data.

The PI or their designated team member will complete the Case Report Form (CRF) as well as all other documents provided by the sponsor (e.g., treatment management documents).

A CRF was designed to record the data required by the protocol and collected by the researcher at each visit.

In the case of self-assessment questionnaires, the principal investigator or the person responsible for completing them is not permitted to modify what was written by the study subject.

Data entry at the center will be performed by the researcher, or a designated person from their team, after completing the Medical Record. The researcher or a designated person from their team will be trained in completing the CRF.

All corrections to the CRF data must be made by the researcher or a designated person on his or her team according to the instructions provided.

To ensure data confidentiality and security, usernames and passwords will be used to restrict system access to authorized personnel only.

The monitor must ensure that all information on the CRF has been completed. After comparing the data with the source documents, the monitor will ask the investigator to make any necessary corrections or clarifications so that the responses and closure can be completed as quickly as possible.

The Scientific Committee of Laboratorios Sophia , SA de CV will conduct the final medical-scientific review and issue guidelines for freezing the database.

8.3 Statistical methodology

8.3.1 Analysis of primary and secondary outcome variables

Statistical analysis will be performed by Sophia Laboratories staff . SPSS version 19 (IBM Corporation , Armonk , NY, USA) will be used.

The designated personnel will be blinded to the intervention groups. Coding will be performed using consecutive numbers for each intervention group.

The data will be collected and organized in an Excel spreadsheet. They will then be exported to the SPSS software platform. The variables will be categorized according to their nature.

The results of continuous quantitative variables will be expressed and presented using measures of central tendency and dispersion (mean, standard deviation, and ranges , as appropriate). Nominal and ordinal qualitative variables will be presented using frequencies, proportions, and/or percentages. See **Table 5Scales to be**

Kolmogorov-Smirnov test will be performed to determine whether the distribution is normal in the results obtained in each study group [50].

The statistical analysis of continuous **quantitative variables** to find significant differences (*p*) will be as follows:

- Intra-group analysis : will be determined by the Wilcoxon rank test, for quantitative variables [51]
- Between-group analysis : Kruskal-Wallis test [52]. This nonparametric test is used to determine whether a group of data comes from the same population. Intuitively, it is identical to ANOVA with the data replaced by categories. For quantitative variables, the Student t *statistic is used* .

The level of difference to consider significance will be an alpha of 0.05 or less.

The results of the nominal and ordinal qualitative variables will be presented as frequencies, proportions, and percentages. See Table 1 (section 6.4.3).

Statistical analysis to identify significant differences in **qualitative variables** will be performed by creating 2x2 contingency tables and will be carried out as follows:

- Intra-group difference : McNemar [53]'s test . This test is applied to 2x2 contingency tables with a dichotomous trait, with matched subject pairs, to determine whether the row and column marginal frequencies are equal (marginal homogeneity).
- Difference between groups : Pearson's χ^2 test (or Fisher's exact test).

The level of difference to consider significance will be an alpha of 0.05 or less.

For adverse event reporting, all eyes of participants randomized to an intervention group after the baseline visit will be considered. Results will be expressed as the number of cases (eyes).

The final results report will be displayed in tables or graphs, as appropriate.

The investigational drug will be considered safe and tolerable when there are no clinical or statistical differences in all primary outcome variables compared to its comparators.

Subjects with an adherence rate greater than 60% will be included in the statistical analysis to meet the study objective, based on the subject's diary. However, even if the subject's diary indicates adherence greater than 60%, if the adherence calculated by weight is less than 30%, the subject will not be included. The minimum dose necessary to obtain a pharmacological effect (lubricant/1 gel application per day) and the presence of adverse events (exposure) were considered sufficient to meet the overall design objective, in accordance with the pharmacological characteristics of the investigational product.

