Creation date: february 2017

Phase I clinical study to evaluate the safety and tolerability of PRO-165 ophthalmic gel versus Artelac® Nightime Gel on the ocular surface of ophthalmologically and clinically healthy subjects

Protocol code:SOPH165-0217/I

Protocol version:4.0

Version date: 21/Jan/2022

Clinical Trial ID: NCT04704531

Sponsor: Laboratorios Sophia, S.A. de C.V.

1. Summary

Title of the study:	
Estudio clínico fase I, para evaluar la seguridad y tolerabilidad del gel oftálmico PRO-165 versus Artelac® Nightime Gel, en la superficie ocular de sujetos oftalmológicamente y clínicamente sanos.	
Protocol code: SOPH165-0217/I	Creation date: February 7, 2017
Protocol version: 4.0	Version date: January 21, 2022
Therapeutic indication: Eye lubricant	
Study period: 4 months	Development phase: I
Aim: To evaluate the safety and tolerability of the PRO-165 formulation on the ocular surface of ophthalmologically and clinically healthy subjects.	
Hypothesis: PRO-165 ophthalmic gel presents a safety and tolerability profile similar to Artelac® Nightime Gel in ophthalmologically and clinically healthy subjects.	
Methodology: Phase I, controlled, parallel-group, double-blind, randomized, exploratory clinical study.	
Number of patients: 32 subjects, divided into 2 groups [16 subjects (16 eyes) exposed per group]	
Diagnosis and main inclusion criteria: 
 - Systemically and ophthalmologically healthy subjects - Signed informed consent. - Age between 18 and 45 years. - Both sexes - Blood tests [complete blood count (CBC), three-element blood chemistry (BC), and liver function tests (LFTs)] within normal parameters - Visual capacity 20/30 or better 	
Test product, dose and route of administration, 
 - PRO-165 Sodium hyaluronate 0.2% ophthalmic gel. Manufactured by Laboratorios Sophia , SA de CV, Zapopan, Jalisco, Mexico. 
 ▪ Dosage: One drop of gel, 4 times a day during the waking period, in the fornix of the right eye. 	

▪ Route of administration: ophthalmic
Treatment duration: 10 days
Reference product, dosage and route of administration:

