6.3 Intervention

6.3.1 Treatments administered

6.3.1.1 Treatment under study

- **PRO-165**
 - Active ingredients (lubricant): sodium hyaluronate 0.2%
 - Pharmaceutical form: Ophthalmic gel
 - Prepared by: Laboratorios Sophia , SA de CV
 - Dosage: One drop of gel, 4 times a day during the waking period, in the fornix of the right eye.

- Formulation description: Clear gel, free of visible particles.
- Packaging description: Sterile multi-dose tube, low-density polyethylene and aluminum polylaminate with high-density polyethylene cap.

Table 4Qualitative -quantitative formulation of PRO -165

Agent type	Amount mg/ mL	Function
Sodium hyaluronate	2.0	Active ingredient
Chondroitin sulfate	Not shown	Viscosant
Polyoxylated Castor Oil 35	Not shown	Solubilizer
Polyethylene glycol 8000¹	Not shown	Cosolvent
Eddate disodium dihydrate	Not shown	Chelating agent
Cetrimide	Not shown	Conservative
Glycerin	Not shown	Osmoregulator
Sodium hydroxide	Not shown	pH adjustment
Homopolymer carbomer type B²	Not shown	Gelling agent
Polycarbophil³	Not shown	Gelling agent
Water for the preparation of injectables cbp⁴	Not shown	Vehicle

Qualitative and quantitative formulation of the investigational product PRO-165. The concentration of the active ingredient is shown, as well as the substances that act as additives. (1) Synonym of Carbowax® (2) Synonym of Carbopol® 974P NF Polymer, USP (3) Synonym of Noveon® AA-1 Polycarbofil, USP (4) as much as is sufficient for

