6.3.1.2 Reference treatment

- **Artelac® Nightime Gel**
- Active ingredients: Carbomer 0.2%
- Pharmaceutical form: Ophthalmic gel
- Prepared by: [name] Chem Pharm. Fabrik GmbH [name] . Imported and marketed by: Bausch & Lomb México, SA de CV, [name].
- Dosage : One drop of gel, 4 times a day during the waking period, in the fornix of the right eye.
- Solution description: Clear gel, free of visible particles.
- Packaging description: Sterile multi-dose tube.
- Characterization: The characterization, stability, and formulation of the comparator will be supported by its packaging, lot number, and IPP, a copy of which will be kept in the study's master folder.

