With a statistical confidence of 95% that corresponds to type I error, equal to 1.96, with a power of 90%, corresponding to type II error, equal to 0.84.

According to the previous calculation, the result is 26 subjects, which was increased by 20% due to the probable losses. The total sample size required is **32 subjects**. So each group will be made up of 16 subjects, who will provide an eye for the analysis.

Analysis Plan [4]

Outcome Variables

Safety primary outcome variables:

- Incidence of Adverse Events.

Primary outcome variables of tolerability:

- ICO score.

Secondary Outcome Variables:

- Tear film rupture time (LRT).
- Vital signs: HR, RF and SAP.
- Posterior segment.
- Quality questionnaire.
- Intraocular pressure.
- Visual capacity.
- Laboratory Tests: BHc, QS, PFH.
- Ocular surface stains.

Table 2. Operational Definition of the Variables

Chondroitin Sulfate 0.18%/Sodium Hyaluronate 0.2%

Variable	Conceptual Definition	Operational Definition	Measurement Type	Normal value	Statistical test
Adverse events (AEs).	Any undesirable medical event that may occur in an investigational subject during the clinical research stage of a drug or vaccine but does not necessarily have a causal relationship with it. ⁴	Adverse events manifested during the conduct of the study will be collected using the CRF.	
 - Continuous quantitative. - Categorical qualitative. 	
 - Frequency: Subjects with AEs/Total number of exposed subjects. - Intensity: 0= Mild 1= Moderate 2= Severe - Causality: 0= Improbably related. 1= Probable or possibly related. 2= Related 	
 - Pearson's square chi or Fisher's exact. - U for Mann-Whitney.
Changes in Intraocular Pressure (IOP).	Tonometry is the objective measurement of IOP, based primarily on the force required to flatten the cornea or the degree of corneal indentation produced by a fixed force.	Goldmann tonometry. 3 samples will be taken, which will be recorded in the clinical file and the average will be recorded in the CRF.	
 - Continuous quantitative. 	
 - 11-21 mmHg. 	
 - U for Mann-Whitney. - Wilcoxon Ranges.

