- Intra-group difference: McNemar test. This is applied to 2x2 contingency tables with a dichotomous feature, with pairs of paired subjects, to determine if the marginal frequencies of row and column are equal (marginal homogeneity).
- Difference between groups: Pearson's Chi-square (χ^2) test or Fisher's exact test at expected values less than 5.

The level of difference to consider significance (p) will be an alpha (α) of 0.05 or less.

Chondroitin Sulfate 0.18%/Sodium Hyaluronate 0.2%

For the reporting of adverse events, all eyes of those participants who were randomly assigned to an intervention group after PI instillation (ITT) will be considered.

The final report of the results will be shown in tables or graphs, as appropriate.

Those subjects who meet a minimum adherence of 60% will be included in the statistical analysis to meet the objective of the study, taken from the subject's diary. However, even if the subject's adherence is greater than 60% per diary, if the adherence calculated by weight is less than 30%, the subject will not be included.

The investigational drug will be considered safe and tolerable when there are no clinical and statistical differences in all primary outcome variables, with respect to its comparator (Artelac® Nighttime Gel).

Table 3. Triangulation of concepts

Variable Type	Variable	A1	B1	B2	C1	D1	E1	E2	E3	E4	E5	E6	E7	E8
Background														
A1	Demographic			DT										
Basal														
B1	Medical History		DT			T								
B2	Comprehensive ophthalmological evaluation		DT	DT		TB			TB		B	B		T
Safety														
C1	Incidence of AD			TB	TB		TB	TB	TB		TB	TB	TB	TB
Tolerability														
D1	ICO			DB			DB							
Secondary outcome														
E1	TRL			DB		TB		DB						
E2	Vitals			DB		TB			B					

Chondroitin Sulfate 0.18%/Sodium Hyaluronate 0.2%

E3	Posterior segment	DB	TB	B
E4	Quality Questionnaire			TB
E5	PIO	DB	TB	B
E6	Visual Ability	DB	TB	B
E7	Laboratory tests	DB	TB	B
E8	Ocular surface stains	TB	TB	TB

D. Descriptive Statistics; T, 2x2 contingency table; B, Bivariate Analysis; M, Multivariate Analysis.

Changes

1. First version of the document, no changes apply.

Author of the document

Ph.D. in Cs. [name].

Biostatistics.

Clinical Operations.

Laboratorios Sophia, S.A. de C.V.

[name]

[name]

References

<https://doi.org/10.1007/BF03163747>.

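### The primary adverse-event outcome is defined in two units, eyes and subjects, and the eye rule does not say that only the treated right eye counts

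*Protocol*

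**What the plan says.** **Unit, by eye.** Protocol 8.3.1: "For adverse event reporting, all eyes of participants randomized to an intervention group after the baseline visit will be considered". The next sentence sets the display: "Results will be expressed as the number of cases (eyes"). The SAP, under Methods of Analysis, repeats the eye wording: "all eyes of those participants who were randomly assigned to an intervention group after PI instillation (ITT) will be considered".

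**Unit, by subject.** SAP Table 2 defines the AE outcome as "Frequency: Subjects with AEs/Total number of exposed subjects", and in the same row attaches the chi-square or Fisher test to it.

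**Treated eye.** Protocol 6.3.1.1 gives PRO-165 "4 times a day during the waking period, in the fornix of the right eye". Section 6.3.1.2 gives the reference gel in the same eye: "One drop of gel, 4 times a day during the waking period, in the fornix of the right eye".

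**Eyes in the sample size.** The protocol Summary plans "32 subjects, divided into 2 groups [16 subjects (16 eyes) exposed per group"]. Protocol 6.6 and 6.6.1 and the SAP sample-size sections agree that each subject contributes one eye, without saying which.

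**What is recorded.** Visual capacity (6.4.3.1) and ocular surface staining are assessed in both eyes. The AE form records left and right eye (9.3.1.1). Item G of 9.3.1.3 allows that AEs may be systemic.

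**Decision rule.** Protocol 8.3.1: "The investigational drug will be considered safe and tolerable when there are no clinical or statistical differences in all primary outcome variables" relative to the comparator. The SAP has the same rule.

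**The concern.** AE incidence is one of two primary outcomes, and the gel is declared safe and tolerable when no difference appears on either. A primary outcome needs one unit fixed in advance. Here the protocol gives eyes, SAP Table 2 gives subjects and the SAP text gives eyes again, so the SAP does not settle the matter.

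Followed literally, the eye rule has three problems:

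- Untreated left eyes could enter the denominator and dilute a difference that exists only in treated eyes.
- Two affected eyes of one subject could be counted as independent observations, which overstates the evidence.
- A systemic AE belongs to no eye and so has no place in the count.

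If nothing is fixed beforehand, the choice of unit can be made after the data are seen.

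**Working it through.** **1. The plan's own denominator.** Protocol 6.6.1 takes 26 subjects plus 20%: 26 × 1.2 = 31.2, rounded up to 32. At 1:1 allocation, 32 / 2 = 16 subjects per arm. One eye each gives 16 eyes per arm, which matches the Summary. With one eye per subject, the eye and subject denominators are the same. They part only if both eyes are counted: 16 × 2 = 32 eyes per arm. Neither document states 32 eyes; it is assumed below to show what the literal wording would do.

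**2. Test.** The SAP uses Fisher's exact test when expected values are below 5 and Pearson's chi-square otherwise, at alpha 0.05. With equal arms the smallest expected count here is half the total number of cases.

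**3. Dilution: 0 v 5 cases, all in treated eyes.** Expected count 5 / 2 = 2.5, so Fisher applies. The two-sided p is twice the probability of the observed table.

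- 16 v 16: 2 × C(16,5) / C(32,5) = 2 × 4,368 / 201,376 = 0.043.
- 32 v 32: 2 × C(32,5) / C(64,5) = 2 × 201,376 / 7,624,512 = 0.053.

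**4. Inflation: 4 v 0 subjects, both eyes affected.** Expected count 2 by subject and 4 by eye, so Fisher applies to both.

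- By subject, 16 v 16: 2 × C(16,4) / C(32,4) = 2 × 1,820 / 35,960 = 0.101.
- By eye, 8 v 0 on 32 v 32: 2 × C(32,8) / C(64,8) = 2 × 10,518,300 / 4,426,165,368 = 0.005.

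**5. False-difference rate in the extreme case.** Suppose the arms have the same true rate, 10% to 50% of subjects affected, and every event is bilateral. Subjects affected per arm are Binomial(16, rate), and affected eyes are twice that out of 32. Summing the binomial probabilities of all tables with p ≤ 0.05 gives:

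| Test | By eye | By subject |
|---|---|---|
| SAP rule (Fisher if an expected count is below 5, otherwise uncorrected Pearson) | about 12.5% to 21.5% | 0.7% to 5.0% |
| Fisher throughout | 9% to 12% | 0.7% to 2% |

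**6. What the subject unit costs.** Assume treated-eye AE rates of 10% v 50%, left-eye events in 10% of subjects in both arms, and independent eyes. The rate of subjects with any AE is then 1 − 0.90 × 0.90 = 19% v 1 − 0.50 × 0.90 = 55%. Exact power under the SAP test rule is about 67% for right-eye events (16 v 16), 55% for subjects with any AE, and 52% for all eyes (32 v 32). The subject unit solves the counting problem but recovers little of the dilution. A right-eye table does recover it.

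All AE rates and laterality patterns in steps 3 to 6 are assumptions. The documents give none.

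**The case against.** The strongest reply is that this is loose wording. Both documents plan 16 exposed eyes per group, dosing is in the right eye only, and one eye per subject enters the analysis, so the study eye can be inferred and the two units share a denominator of 16. The sentence in 8.3.1 is also about reporting. It may serve only to keep every randomized participant in the AE tables, in contrast to the adherence filter later in that section, and the SAP tags it as ITT. Table 2, where the AE tests are attached to a frequency, counts subjects.

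Most of this stands, and it is why the intent is probably harmless. It does not close the gap. The inference about the eye is the reader's, since neither rule names it. Left-eye events will be recorded, and neither they nor systemic events have a stated place under the one-eye reading.

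Two stronger readings are tempting and not supported:

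- A reader might infer that the sponsor plans to test 32 eyes per arm. Neither document says so, and the sample-size text points the other way.
- A reader might infer that the unit alone can reverse the safety conclusion. The rule also requires no clinical difference, so a 0 v 5 imbalance could still count against the gel at p = 0.053.

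The all-bilateral case is an extreme for a gel given in one eye. It bounds the problem and is not a forecast.

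**Conclusion.** The point holds as an inconsistency in the definition of a primary outcome that should be corrected. The two units are in the text, the SAP contradicts itself, and the eye rule leaves laterality and systemic events unassigned.

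The size depends on a literal reading that neither document states. On that reading the unit can move a Fisher p-value across 0.05 in either direction. In the extreme bilateral case the false-difference rate by eye reaches about 12.5% to 21.5%, where the subject rule stays at or below 5.0%. If the rule means one study eye per subject, these effects vanish for events in that eye, and what remains is where left-eye and systemic AEs are counted. The plan should state which reading applies before the data are analysed.

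**What to change.** In protocol 8.3.1 and the SAP text:

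- Replace the eye rule with the SAP Table 2 definition: subjects with at least one AE over exposed subjects, by arm, in all randomized and exposed participants. Name this as the one unit for the no-difference rule.
- Add a supportive between-arm table of ocular AEs in the treated right eye over exposed subjects.
- List left-eye and systemic AEs separately.
- State that ocular measures recorded eye by eye are analysed from the right eye.

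**Cost.** A protocol amendment and a SAP revision. No new data are needed, because the AE form already records the eye, and the sample size does not change. The drawback is that left-eye and systemic events counted in the subject rule can dilute a right-eye difference (about 55% against 67% power in the example above), which is why the right-eye table should accompany it.

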5.5.2 Specific objectives

- To describe the safety of PRO-165 ophthalmic gel by presenting adverse events.

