5.5.4 Hypothesis

H_0 PRO-165 ophthalmic gel presents a safety and tolerability profile similar to Artelac® Nighttime Gel in ophthalmologically and clinically healthy subjects

H_1 PRO-165 ophthalmic gel presents a different safety and tolerability profile than Artelac® Nighttime Gel in ophthalmologically and clinically healthy subjects.

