6.6 Sample size

A total size of 32 subjects is estimated, distributed in 2 intervention groups. [16 subjects (16 eyes) per group]

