The data will be collected and sorted in an Excel spreadsheet (Microsoft® Office). The data will then be exported to the SPSS program platform. The variables will be categorized according to their nature (see [Table 2](#)).

Study participants will be identified by a number and their initials.

The initials of the study subject will be obtained starting with the first letter of the name, followed by the first letter of the first surname and the first letter of the second surname, obtaining a maximum of three letters, in case the person has two names or compound surname, the first letter will always be used.

Example:

To. [name]	B. [name]
to. Initials: AMC	b. Initials: JDO

Once the subject has been selected, they will be assigned a number with which they will be identified throughout the study. This code will be made up of eight numbers in the following order from left to right:

- Three digits of the molecule under study according to the name by the sponsor.
- Two digits corresponding to the research centre number.
- Three digits of the number following their inclusion assigned to the research centre.

The results of the continuous quantitative variables will be presented in measures of central tendency: mean, standard deviation and ranges, see [Table 2](#).

The Kolmogorov-Smirnov and Shapiro Wilk test will be performed to determine the type of distribution of the data (normality) in the results obtained in each study group. [5]

The statistical analysis of the continuous quantitative variables to find significant differences (p) will be as follows:

- Intra-group analysis: will be determined by Wilcoxon's rank test, for quantitative variables. [6]
- Inter-group analysis: Differences between groups will be analyzed using the Mann-Whitney U statistic.

The level of difference to consider significance will be an alpha (α) of 0.05 or less. A 95% CI will be considered for the non-inferiority criteria.

The result of the nominal and ordinal qualitative variables will be presented in frequencies, proportions and percentages, see [Table 2](#).

The statistical analysis to identify significant differences in the qualitative variables will be carried out by creating 2x2 contingency tables and will be carried out as follows:

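### Declaring PRO-165 safe and tolerable when 16 per arm show no significant difference treats absence of evidence as evidence of similarity

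*Protocol*

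**What the plan says.** The two primary variables are adverse events (safety) and the eye comfort index (tolerability). Protocol section 8.3.1 says the investigational drug "will be considered safe and tolerable when there are no clinical or statistical differences in all primary outcome variables" relative to its comparators. The SAP, under Methods of Analysis, repeats it with a different connective: "The investigational drug will be considered safe and tolerable when there are no clinical and statistical differences in all primary outcome variables". Neither document gives another success criterion.

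The surrounding text is:

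- **Hypotheses (protocol 5.5.4).** Similarity to Artelac is H0. H1 is that PRO-165 "presents a different safety and tolerability profile than" the comparator.
- **Size (protocol 6.6).** "16 subjects (16 eyes) per group".
- **Tests.** The significance level is 0.05. For qualitative variables protocol 8.3.1 allows Pearson's chi-square or Fisher's test without saying when each applies. The SAP specifies "Fisher's exact test at expected values less than 5". For quantitative variables the SAP says: "Differences between groups will be analyzed using the Mann-Whitney U statistic".
- **Non-inferiority.** One SAP sentence: "A 95% CI will be considered for the non-inferiority criteria". It gives no margin and no endpoint, and the conclusion rule does not use it.
- **Objective (protocol 5.5.2).** "To describe the safety of PRO-165 ophthalmic gel by presenting adverse events". The study is labelled exploratory.

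**The concern.** A non-significant test shows that the data are compatible with no difference. It does not show that a material difference is absent, and with 16 per arm it will often be compatible with both. Because similarity is H0, the rule rewards low power: the fewer subjects analysed, the easier the statistical part is to pass.

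The clinical part could stop a bad result, but neither document gives it a threshold, an assessor or a procedure. The change from *or* to *and* between the documents also leaves unclear whether, under the SAP, a clinical difference alone would defeat the claim.

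At stake is the headline conclusion. A study set up to describe safety would issue a positive statement that its data may not support, and nothing in the written rule obliges anyone to notice.

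**Working it through.** **Inputs from the documents.** 16 per arm and 1:1 allocation (protocol 6.6.1, 7.1); alpha 0.05, taken as two-sided because 6.6.1 uses z = 1.96; test choice from the SAP. The plan states no error rates for its conclusion rule, so there is none to reproduce. Its size does follow from its own base figure: 26 × 1.2 = 31.2, rounded up to 32, or 16 per arm. (The 26 is a separate matter. With p = 0.10, p0 = 0.25, the stated z-values and delta = 0, the formula gives 0.09 × (2.80/0.15)² = 31.4. No delta is given. Nothing below depends on this.)

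**Assumption.** The documents give no adverse event rate for Artelac, so a range of 5% to 20% is used.

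**Step 1: chance that the adverse event test is non-significant.** Let X ~ Bin(16, p_T) for PRO-165 and Y ~ Bin(16, p_C) for Artelac. Sum P(X = x)·P(Y = y) over all 17 × 17 outcomes with p > 0.05. With equal arms the smallest expected count is half the total events (or half the non-events, if fewer), so the SAP rule uses Fisher when there are fewer than 10 events.

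| Comparator | PRO-165 | SAP rule | Fisher throughout | Uncorrected chi-square |
|---|---|---|---|---|
| 5% | 15% | 96% | 96% | 90% |
| 5% | 20% | 90% | 90% | 79% |
| 10% | 30% | 82% | 83% | 70% |
| 10% | 40% | 59% | 64% | 45% |
| 15% | 45% | 60% | 69% | 51% |
| 15% | 60% | 24% | 36% | 21% |
| 20% | 60% | 35% | 50% | 33% |
| 20% | 80% | 4% | 9% | 4% |

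At 13 per arm (the 26 subjects before the allowance for losses) and a 10% comparator, the SAP rule gives 88% for a threefold rate and 72% for a fourfold rate.

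**Step 2: what passes.** Under the SAP rule the smallest flagged results are 5 v 0 (p = 0.043), 7 v 1 (p = 0.037) and 8 v 2 (p = 0.022; expected count exactly 5, so chi-square). The results one event below all pass: 4 v 0 (p = 0.101), 6 v 1 (p = 0.083) and 7 v 2 (p = 0.113). Uncorrected chi-square, which the protocol also permits, would flag all three (p = 0.033, 0.033, 0.049).

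**Step 3: what those results leave open.** The Newcombe interval combines the Wilson limits (l, u) of each arm:

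- lower = d − √[(p1 − l1)² + (u2 − p2)²]
- upper = d + √[(u1 − p1)² + (p2 − l2)²]

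For 6/16 and 1/16 the Wilson limits are 0.185 to 0.614 and 0.011 to 0.283, and d = 0.3125.

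- lower = 0.3125 − √(0.190² + 0.221²) = 0.02
- upper = 0.3125 + √(0.239² + 0.051²) = 0.56

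For 0/16 v 0/16 each Wilson upper limit is 3.84/(16 + 3.84) = 0.194, so differences of up to 19 points in either direction remain open. For 2/16 v 2/16 it is 25 points.

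**Step 4: comfort index.** No SD is documented. Assuming a normal shift, 100,000 simulations of the Mann-Whitney test at 16 per arm give power 0.257 at 0.5 SD, so such a difference is missed about 74% of the time. Power reaches about 0.80 only at 1.06 SD. The test's size is 0.046.

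**Step 5: both primary variables together.** If the comfort index is truly equal and independent of adverse events, both tests are non-significant with probability 0.816 × 0.954 = 0.78 (threefold, 10% comparator) or 0.588 × 0.954 = 0.56 (fourfold).

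**The case against.** The strongest points on the other side are these.

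- **The comparator rate is assumed.** Any pathological finding on a full eye examination is reportable as an adverse event (protocol 6.4.3.4), so rates above 10% are plausible, and at 20% the test detects large ratios well. This stands as a limit on the size, not on the logic.
- **The test matters.** At 40% v 10%, uncorrected chi-square misses the difference in only 45% of trials, and it would flag 6 v 1. This stands for the protocol's open choice. The SAP's expected-count rule sends 6 v 1 to Fisher.
- **More than one adverse event test may count.** SAP Table 2 lists intensity and causality beside frequency. If every comparison must be non-significant, the percentages above are upper limits for passing the statistical part. This stands, but extra tests are not a similarity criterion.
- **The 13-per-arm figures are one reading.** Adverse event reporting covers all randomised participants (in the SAP, after instillation). Losses reduce that comparison only if the adherence or visit 1 restrictions are applied to it.
- **Other safeguards exist.** Intensity and causality are recorded, serious events above 5% in a group prompt consideration of stopping, and a sponsor committee carries out the final medical review. None of these defines a clinical difference for the conclusion rule.
- **The comfort index figures are approximate.** The score is bounded and probably low in healthy subjects, so normality is doubtful, and without an SD the results cannot be expressed in points.
- **It is a small exploratory Phase I study.** That argues for a descriptive conclusion, which the current rule does not give.

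**Conclusion.** The concern holds. The only success rule in either document treats non-significance at 16 per arm, plus an undefined clinical check, as proof of safety and tolerability. This is wrong at any event rate. Its practical size depends on the assumed comparator rate: under the SAP's test, a threefold rate goes undetected in at least 82% of trials and a fourfold rate in at least 59% when the comparator rate is 10% or less. The problem shrinks quickly above that. These figures cover a single comparison of the proportions with adverse events, two-sided at 0.05, with all 32 subjects analysed; they do not include whatever the clinical check might catch. The rule must be changed before unblinding.

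**What to change.** In protocol 8.3.1 and in the SAP, remove the rule and instead:

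1. Report the PRO-165 minus Artelac difference in the proportion of subjects with adverse events, with a 95% Newcombe or exact interval, and the difference in the comfort index with a 95% interval.
2. State the conclusion descriptively: no signal seen, differences up to X not excluded, with X read from the interval. Say explicitly that p > 0.05 is not taken as evidence of safety or similarity.
3. If a clinical difference is kept as a criterion, fix before unblinding what size counts and who decides, and use the same wording in both documents.
4. Delete the SAP's non-inferiority sentence, unless the sponsor fixes an endpoint and a margin before unblinding and claims non-inferiority only when the unfavourable confidence limit lies inside that margin.

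The cost is wording in two documents and two intervals; subjects, visits and data collection do not change. The claim becomes weaker. The margin option is rarely attainable at this size: with truly equal 10% rates, the Newcombe upper limit falls inside a 20-, 15- or 10-point margin in 37%, 23% or 11% of trials (51%, 26% or 9% at equal 5% rates). Descriptive reporting is therefore the better choice, and it matches the stated objectives.
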